5.6.2 Key secondary endpoints

All key secondary endpoints will be presented using the mITT and PPS populations.

Clinical Impression of Change in Severity

The CI-CS scores on the pre-defined anchor test for Visit 4 versus Visit 2, and the CI-CS score on the pre-defined anchor test for Visit 6 versus Visit 4 will be evaluated separately. These key secondary endpoints will be summarized using descriptive statistics and frequency tables, and percentages will be shown graphically using a bar chart. No sensitivity analysis will be applied.

Change in severity score based on Averaged Clinical Impression of Severity (CI-S)

CI-S scores are measured on a 7-point Likert-point scale (-3 = among the most extremely ill patients to +3 = normal, not at all ill; see Section 5.2 for the precise definition) and the primary endpoint is defined as the difference between both CI-CS scores.

Improvement in the pre-defined anchor test measure will be evaluated based on the change in the blinded raters' CI-S scores between the baseline period (average for Visit 1 and Visit 2) and end of treatment period (average for Visit 3 and Visit 4) minus the change in CI-S between end of treatment period (average for Visit 3 and Visit 4) and end of washout period (average for Visit 5 and Visit 6). Note that if a CI-S score is missing at one visit for a period, but available at the other visit in the same period, that one value will be used instead of the average. If both videos in a period are missing, then we cannot determine the average and the period will be assigned a value of 0 (stable). The presentations and statistical analyses will be similar to the primary endpoint, excluding the sensitivity analysis which is only to be used for the primary endpoint. Data received for non-anchor CI-S scores will only be listed.

Clinical Impression of Change in Severity reclassified on a 3-point scale

Using the CI-CS outcome on the pre-defined anchor test based on the data for Visits 2 and Visit 4, any patient given a score <0 on the CI-CS will be classified as worsened (-1). Any patient classified as 0 on the CI-CS will be classified no change (0). Any patient given a score >0 on the CI-CS will be classified as improved (+1). Similarly, the CI-CS comparing Visit 4 and Visit 6 will be reclassified and the differences between these two scores on a 3-point scale will be calculated.

The descriptive table and graphical presentations will be similar to the primary endpoint. No statistical analysis will be performed, and no sensitivity analysis will be applied.

Clinical Impression of Change in Severity (CI-CS) score non-primary anchor test

Descriptive statistics and frequency tables of the CI-CS scores for the test (9HPT-D or 8MWT) that was not selected as the primary anchor test will be presented for Visit 4 versus Visit 2, and separately, for Visit 6 versus Visit 4. No plots will be created, and no sensitivity analysis will be applied.

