8.6 Missing Data

The primary endpoint will utilize assessments based on single video recordings at the end baseline period (Visit 2), end of the treatment period (Visit 4), and end of the washout period (Visit 6). If the Visit 2 video is missing, the Visit 1 video will be used in its place. Similarly, if the Visit 4 and Visit 6 videos are missing, Visit 3 and Visit 5 videos will respectively be used in their place.

Analyses based on the mITT analysis set will utilize a last observation carried forward (LOCF) approach for missing videos at Visit 5 and Visit 6. For the primary endpoint CI-CS, this implies

¹⁶The 9 Hole Peg Test of the Dominant Hand (9HPT-D) and the 8 Meter Walk Test (8MWT), will be videoed for every patient at every visit except Visit 0

¹⁷ European Sites Only

that the CI-CS value for **Visit 4** to **Visit 6** will be assigned the value 0 (stable) if both videos at Visit 5 and Visit 6 are unavailable.

A sensitivity analysis will be undertaken to assess the robustness of the primary analysis of the primary endpoint in the mITT analysis set as follows:

If either video for Visit 3 or Visit 4 is available, but either video from Visit 5 and Visit 6 are unavailable, impute the value -1 (worsening) instead of 0 for the CI-CS for Visit 4 to Visit 6, unless the missingness is due to a "technical reason" (e.g. due to machine failure).

Additional methods to deal with missing data will be detailed in the SAP. Any changes from the SAP will be described and justified in the Clinical Study Report.

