3.1.2 Modified Intention-to-Treat (mITT) population

The mITT population will consist of all patients who receive at least one dose of study drug (N-Acetyl-L-Leucine) and with one video recording at either Visit 1 or Visit 2 (or both) and one video recording at either Visit 3 or Visit 4 (or both).

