5 PARENT STUDY: STATISTICAL ANALYSIS

5.1 General considerations

The Parent study is considered the study period between screening (Visit 0 or Visit 1) through Visit 6.

Raw data (in listings) will be presented in the same precision as received. Appropriate rounding will be performed for the following summary statistics, where applicable: mean, standard deviation (SD) and two-sided 90% confidence limits will be presented with at least one more decimal than the original data; minimum and maximum values will be presented with the same precision as the original data. In frequency tables, percentages will be presented with 1 decimal unless otherwise stated.

P-values will be presented with 3 decimals, and those smaller than 0.001 will be replaced by <0.001. One-sided p-values smaller than 0.05 will be considered statistically significant for the primary endpoint and indicative for other endpoints. No adjustment for multiple comparisons will be applied. Conclusions regarding treatment efficacy will not solely rely on detecting statistical significance but equal emphasis will be placed on the magnitude and clinical relevance of treatment differences as judged by the point estimates. All evaluations other than the primary endpoint will be considered exploratory in nature.

Descriptive statistics presented in general summary tables will be the number of non-missing observations (n), mean, SD, minimum, median and maximum for quantitative data. For categorical data, frequency counts and percentages will be determined.

In general, baseline is defined as the value measured prior to first study treatment administration (at Visit 2), unless otherwise specified. In case no value at Visit 2 is available, the value measured at Visit 1 will be used. A footnote may be added to those tables/listings presenting baseline value, with an explanation how this value was assessed.

If available in the database, data for screening failures will not be presented in summary tables, except for disposition, medical history and end-of-study displays. Data for screening failures will be listed as available.

A treatment emergent adverse event (TEAE) is defined as an adverse event that appears during or after study treatment and was absent before.

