5.2 Adjudication of endpoint data

Each individual video (CI-S) or video pairing (CI-CS) will be read by two independent reviewers. For the CI-S assessments of the primary and non-primary anchor test, the independent raters will be given 6 videos of the patient's performance taken at Visit 1 to Visit 6. For the CI-CS assessments of the primary and non-primary anchor test, the raters will be given three pairs of videos and asked to score the CI-CS for each video pair. The video pairs will be labeled Video A to Video B, Video B to Video C, and Video C to Video A¹. The videos will be presented in a random order, and the independent raters will be blinded to the timepoint corresponding to each video. The appropriate Likert scale score will be provided to each of the videos and pairs of videos.

^{(2019).} Video Review Charter. IntraBio Ltd. Internal Document.

Clinical Study Reference: IB1001-202

For the CI-CS assessment, pairs of videos will be evaluated with the Likert scale defined as:

- Significantly Improved (Score = +3)
- Much Improved (Score = +2)
- Minimally Improved (Score = +1)
- No Observable Change (Score = 0)
- Minimally Worse (Score = -1)
- Much Worse (Score = -2)
- Significantly Worse (Score = -3)

If there is a scoring difference between the two blinded raters for a CI-CS assessment, the following rules will apply:

- If the difference between the blinded raters is 1, the two scores will be averaged, and the unrounded average value will be used for further analysis.
- If there is a scoring difference of >1 between the two blinded raters for a CI-CS assessment, then a third blinded rater will review the scores and will determine which score is more accurate (adjudication by consensus). The adjudicator's decision will be the final score for that video assessment and used for further analysis.

For the CI-S assessment, individual videos will be evaluated with the Likert scale defined as:

- Normal, not at all ill (Score = +3)
- Borderline ill (Score = +2)
- Mildly ill (Score = +1)
- Moderately ill (Score = 0)
- Markedly ill (Score = -1)
- Severely ill (Score = -2)
- Among the most extremely ill patients (Score = -3)

If there is any scoring difference between the two blinded raters for a CI-S assessment, the two scores will be averaged, and the unrounded average value will be used for further analysis.

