5.6 Statistical analysis efficacy endpoints

The primary analysis population is the mITT for the primary and all secondary endpoints. Analyses of these endpoints based on the PPS will also be undertaken to provide supplementary information on efficacy. The ITT population will be used only for baseline summary tables.

Analyses of the primary endpoint based on the mITT population will utilise a last observation carried forward (LOCF) approach for missing/unreadable videos at Visit 5 and Visit 6. For the primary endpoint CI-CS, this implies that the CI-CS value for Visit 4 to Visit 6 will be assigned the value 0 (stable) if both videos at Visit 5 and Visit 6 are unavailable.

Also for the key secondary endpoint, Change in Severity Score based on Averaged Clinical Impression of Severity (CI-S), it is assumed that if both videos are missing/unreadable for the baseline (Videos from Visit 1 or 2), treatment (Videos from Visit 3 or 4), or washout (Videos from Visit 5 or 6) period, the change from one period to another will be assigned the value 0 (stable).

Clinical Study Reference: IB1001-202

A sensitivity analysis for missing data will be performed for the statistical analyses to compare patient's outcome on the primary outcome measure and their compliance throughout the study. The robustness of the primary analyses in the mITT analysis set will be assessed as follows:

• If either video for Visit 3 or Visit 4 is available but both videos for Visit 5 and Visit 6 are not available, then the value -1 (worsening) will be used instead of 0 for the CI-CS for Visit 4 to Visit 6 unless the missingness is due to a technical reason (MCAR, e.g. due to machine failure).

For each of the primary and secondary endpoints there will be separate descriptive statistical displays within the key subgroups as listed in Section 5.5.3 without any statistical analysis. For the subgroup presentations, only the mITT population will be used. Spaghetti plots will not be created for the subgroup analyses; these will be presented in forest plots (one for each endpoint, excluding the SARA -, SAFI - and mDRS subscores and excluding the EQ-5D-5L/Y), presenting the mean or (pseudo-)median with a 90% two-sided CI, using a stem at mean or median difference of 0, where applicable. Upon discretion of the programmer, the forest plots may be presented as two plots: one for Visit 4 versus Visit 2 and one for Visit 6 versus Visit 4.

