7 CHANGES TO PROTOCOL AND OTHER RELEVANT REMARKS

Instead of Bland-Altman analyses of outcome scores at Visit 1 vs Visit 2, Visit 3 vs Visit 4, and Visit 5 vs Visit 6 as described in the protocol for the Parent study, an ICC method for agreement

Clinical Study Reference: IB1001-202

between the visits will be used instead to assess the stability of the outcome, as described in section 5.6.4. This is because no per-rater information is available in the dataset to be received, only an averaged or agreed value.

Regarding CI-S, the protocol is stating that for each assessment, the videos will be labeled as Video A, B, C, D, E, F. This is however not present in the DTA and test data from and is therefore removed from the SAP.

For Quality-of-Life measures, since the scoring is done for children with the EQ-5D-Y and for adults with the EQ-5D-5L, tabulations and analyses will be done separately for the corresponding age groups. The presentations on the VAS will be combined for children and adults.

For the Parent phase, sparse PK sampling will be collected for biochemical analysis to characterize the pharmacokinetics of N-Acetyl-L-Leucine in patients with GM2 Gangliosidosis. For the Extension phase, full PK profiles will be collected at Visit 7 and Visit 9. Creation of descriptive displays and reporting of these data is outside the scope of this statistical analysis plan. PK concentration data and PK parameters (following a population PK analysis) will be included in SDTM domains, after receipt. For the Parent phase a listing of PK concentration data will be created for inclusion in the Parent phase CSR, since the full PK report will only be available after the end of the Extension phase. Furthermore, urine tests for N-Acetyl-D-Leucine are handled by the same lab but will be included in the clinical database and will therefore be part of the CDISC datasets.

Regarding the sensitivity analysis (imputation of value -1) for missing data in the primary and secondary analyses: this is only applied to the primary analysis of the Parent phase. Regarding the LOCF/assumption of value 0 for missing data: this is only applied to the primary and one key secondary endpoint as specified in the relevant sections in this SAP.

The investigation of the intra-rater correlation cannot be performed, since the **sector** data do not differentiate the data per rater but rather provide an average or agreed value. Therefore, this analysis has been removed from the SAP.

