Age is not collected during the Extension phase, and therefore whenever age is necessary for any calculations or presentations at Extension phase visits, it should be calculated using the respective visit date combined with the date of birth as collected at Visit 1. The same imputation rule as stated above (for calculation of age at diagnosis) will be applied.

Blinded data

The blinded results on the video-recordings (blinded rater's CI-CS and CI-S) will be received from according to the agreed transfer specifications. Recoding needs to be done using the visit schedule provided with the blinded results, since the visit review order is randomly assigned. The LOCF for video comparison is already available in the data.

SCAFI

For 8MWT, assistance of another person or using the wall as support is not allowed. However, timed 8MWT trials for participants who used "unallowable support" (another person or the wall) are entered in the database, considering these measurements are also necessary due to their relation to the primary and a number of secondary endpoints of the study based on videos of the test. Therefore, for the SCAFI analysis, the data for these patients that used either the wall or person support during the 8MWT should be made missing.

Furthermore, patients for 9HPT, the following clinical rules apply:

- if proband cannot complete trial in 5 minutes (i.e. 300 seconds) with dominant hand, move on to the trials with non-dominant hand
- if proband cannot complete one trial in 5 minutes (i.e. 300 seconds) with non-dominant hand, discontinue 9HPT

As a consequence, if in the database values >300 are entered for Trial 1 and/or 2, the approach for handling these data in regards to SCAFI will be:

Clinical Study Reference: IB1001-202

- In the case Trial 1 has a value <300 and Trial 2 has a value of >300 seconds, only the trial 1 with value <300 will be used for further analysis.
- In the case Trial 1 has a value of >300 seconds and Trial 2 has a value of <300 seconds, the data will count as missing and unable to perform due to physical limitations (as per the discontinuation rules defined above, Trial 2 should not have been conducted)
- In other instances, where only one trial is performed with a value >300 seconds, or two trials are performed with both values >300 seconds, the data will be considered missing due to physical limitations and replaced with a missing value for further analysis.

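### SAP 5.6 and 5.6.2 impute a missing CI-S period differently: one sets the change to 0, the other sets the severity score to 0, which means moderately ill

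*SAP*

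**What the plan says.** The endpoint is defined in SAP 5.6.2. It is the change in CI-S from the baseline period to the treatment period, minus the change from the treatment period to the washout period. Each period value averages two visits. It is tested like the primary endpoint, without the sensitivity analysis.

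The SAP says twice what happens when both videos of a period are missing:

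- SAP 5.6, naming this endpoint, sets the difference to zero: "the change from one period to another will be assigned the value 0 (stable".
- SAP 5.6.2 sets the period to zero: "then we cannot determine the average and the period will be assigned a value of 0 (stable".

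SAP 5.2 fixes the meaning of a CI-S score of zero: "Moderately ill (Score = 0". Zero means no observable change only on the other scale, CI-CS, which rates pairs of videos.

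Three other places touch the point. Protocol 8.6 says that mITT analyses "will utilize a last observation carried forward (LOCF) approach for missing videos at Visit 5 and Visit 6". SAP 7 says of the zero imputation that "this is only applied to the primary and one key secondary endpoint as specified in the relevant sections in this SAP". SAP 10.1 adds "The LOCF for video comparison is already available in the data".

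**The concern.** A change and a severity level are different quantities. Assigning zero to a change says the patient did not move. Assigning zero to a CI-S period says the patient was moderately ill in that period, whatever the other videos show. The two sections therefore give different endpoint values for the same patient.

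This endpoint has its own t-test or Wilcoxon result (table 14.2.10 in SAP 11.3) and enters the subgroup forest plots, where small denominators enlarge any shift. Depending on which section the programmer follows, the same data can give two estimates and two p-values.

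An empty washout period is possible in the mITT. SAP 3.1.2 requires a baseline video and "one video recording at either Visit 3 or Visit 4 (or both", but no washout video. Under the COVID-19 provisions of Protocol 3.1.2.5, Visit 5 may be skipped in person and the remote visit that replaces it is not video-recorded. If the Visit 6 video is then also missing, the period is empty.

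**Working it through.** The plan states no figure for this imputation, so there is none to reproduce. The check applies both rules to the endpoint.

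**Inputs.** B, T and W are the CI-S averages for baseline (Visits 1 and 2), treatment (Visits 3 and 4) and washout (Visits 5 and 6), on a scale from −3 to +3 with higher better (SAP 5.2 and 5.6.2). The planned mITT is about 36 and the planned PPS about 30 (SAP 2.4.1). The SD of 1.02 is the planning value for the primary endpoint (SAP 2.4.1); none is given for CI-S.

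**Formula.** E = (T − B) − (W − T).

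- Washout missing: 5.6 sets W − T = 0, so E = T − B. 5.6.2 sets W = 0, so E = (T − B) + T = 2T − B. The difference is T.
- Baseline missing: 5.6 gives E = T − W; 5.6.2 gives E = 2T − W. The difference is again T.
- Treatment missing: 5.6 sets both changes to 0, so E = 0; 5.6.2 sets T = 0, so E = −(B + W).

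| Missing period | Observed | E under 5.6 | E under 5.6.2 |
|---|---|---|---|
| Washout | B = −2, T = −2 | 0 | −2 |
| Washout | B = −2, T = −1 | +1 | 0 |
| Washout | B = 0, T = +1 | +1 | +2 |
| Baseline | T = W = −1 | 0 | −1 |
| Treatment | B = W = −1 | 0 | +2 |

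With washout or baseline missing, the rules agree only if T = 0. Neither is uniformly conservative.

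**Shift in the mITT mean.** If k of 36 patients have no usable washout video, the mean under 5.6.2 minus the mean under 5.6 is k × mean(T) / 36, with mean(T) taken over those k patients. Neither k nor mean(T) is in the documents. The assumed range for k is 1 to 6. The top value is 36 − 30 = 6, the planned gap between mITT and PPS; that gap also contains protocol deviators and rests on approximate planning numbers.

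| k | mean T = ±1 | mean T = −1.5 | mean T = 0 |
|---|---|---|---|
| 1 | ±1/36 = ±0.028 | −0.042 | 0 |
| 3 | ±3/36 = ±0.083 | −0.125 | 0 |
| 6 | ±6/36 = ±0.167 | −0.250 | 0 |

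**Against the standard error.** Borrowing SD 1.02, SE = 1.02/√36 = 0.170. For a mean T of 1 in absolute value, the shift is 0.028/0.170 = 0.16 SE, 0.083/0.170 = 0.49 SE and 0.167/0.170 = 0.98 SE for k = 1, 3 and 6. This holds the SD fixed, although the choice of rule would also change it somewhat.

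**The case against.** The best defence is that the intended rule can be recovered. Only a change can be stable, and 5.6.2 uses that label. Section 5.6 names this endpoint and says the change is set to zero. SAP 7 treats carrying the last observation forward and assuming zero as one device, which makes sense only if the zero is a change. Protocol 8.6 carries forward for missing washout videos, which gives W = T and so a zero change. On this view 5.6.2 contains one loose sentence and not a second rule.

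Most of that is right about intent, and the 5.6.2 wording is probably a slip. It does not remove the problem. Section 5.6.2 is the endpoint-specific section and its literal instruction can be programmed as it stands. SAP 7 sends the reader back to the sections that conflict. The remark in SAP 10.1 most naturally concerns the CI-CS pairs and settles nothing for single-video CI-S scores.

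Two further points stand. The change rule matches carry-forward only for a missing washout: a missing baseline has nothing to carry forward, and carry-forward for a missing treatment period would give B − W, not 0. Also, little depends on the result. SAP 5.1 says "All evaluations other than the primary endpoint will be considered exploratory in nature", SAP 7 ties trial success to the parent primary endpoint, the PPS requires a recording in every period, and individual scores are listed, so a reader could recompute.

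**Conclusion.** The conflict is real, and 5.6.2 as written would impute a severity level where stability is meant. It should be fixed. The textual finding is firm and needs no assumptions.

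The size is uncertain. Per patient with a missing washout or baseline, the discrepancy is T, anywhere from −3 to +3. For the mITT mean it is 0.03 to 0.17 in absolute value for 1 to 6 affected patients with an absolute mean T of 1, and zero if no period is empty or the affected patients average T = 0. The standard-error comparison also rests on an SD borrowed from a different endpoint.

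The primary endpoint is unaffected. The PPS is affected only if every video of a period exists but cannot be read.

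**What to change.** In SAP 5.6.2, replace the sentence that gives the period a value of zero with: if both videos in a period are missing or unreadable, any change to or from that period is assigned the value 0 (stable), as in Section 5.6. State the three consequences: a missing washout gives T − B, a missing baseline gives −(W − T), and a missing treatment period gives 0. The same paragraph also carries a stray sentence defining the primary CI-CS endpoint, which could be removed at the same time.

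Before database lock, confirm that the analysis program applies this rule and, if any CI-S imputation arrives already made in the received data, that it follows the same rule. The documents do not show whether the parent database is already locked. If it is, record in the study report which rule was applied and how many patients it touched.

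The cost is one SAP sentence and one program check.
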